3.2.4.2. Laboratory Data

Safety laboratory tests (hematology, chemistry, and other clinical laboratory tests) will be performed as described in the protocol.

To determine if there are any clinically significant laboratory abnormalities, the safety laboratory tests will be assessed against the criteria specified in the sponsor reporting standards. The assessment will take into account whether each participant's baseline test result is within or outside the laboratory reference range for the particular laboratory parameter.

3.2.4.3. Vital Signs

A single measurement of pulse rate and supine systolic and diastolic blood pressure (BP) will be taken at the times specified in the protocol.

Change from baseline will be calculated for all post-baseline timepoints.

3.2.4.4. Electrocardiograms (ECGs)

A single standard 12-lead ECG will be collected at times specified in the protocol.

Change from baseline for ECGs (heart rate, QT, QTcF, PR and QRS interval) will be calculated for all post-baseline timepoints.

3.3. Other Safety Endpoint(s)

See Section 3.2.4.

3.4. Other Endpoints/ Exploratory Endpoints

3.4.1. Change from baseline in additional physical activity and gait endpoints measured with remote digital sensors at Week 12

See Section 3.2.1.

The additional physical activity and gait endpoints are:

From the wrist device:

- Light, Moderate, Vigorous Activity Time (mins/day)
- Number of Steps per Day (steps/day)
- Sleep Time (mins/day)
- Calories (cal)
- Max 15/60 mins of activity level (M15mins, M60mins; au/day)
- Average activity counts for the most active 10 hours of the day (M10hr; au/day)
- Average activity counts for the least active 5 hours of the day (L5hr; au/day)

From the lumbar device:

- Stride Duration (s)
- Double Support Duration (s)
- Single Limb Support Duration (s)
- Stance Duration (s)
- Swing Duration (s)
- Stride Lengths (m)
- Number of Steps (Average Cadence) (steps/min)
- Total Number of Steps per Day (steps/day)

3.4.2. Change from baseline in additional FAACT total and sub-scale scores at Week 12

See Section 3.2.2

The additional FAACT total and sub-scale scores are:

- Physical Well-being (PWB)
- Social/Family Well-being (SWB)
- Emotional Well-being (EWB)
- Functional Well-being (FWB)
- FACT-G Total score
- FAACT Total score

3.4.3. Serum unbound and total concentrations of ponsegromab on Day 1, Weeks 4, 5, 8, 10, 12, and 16 (follow-up), plus Week 9 and 11 in PK substudy only

Blood samples will be collected for measurement of serum unbound and total concentrations of ponsegromab as specified in the protocol. The PK sample collection at the Week 5 visit is considered an optional sample and it will not be considered a protocol deviation if the participant is unable to make this visit. In addition, if a participant has an unplanned site visit for any reason, (chemotherapy, radiology, other doctor appointments, etc.), a PK sample may be collected, if feasible.

Trough concentrations (C_{trough}) are defined as the samples measured pre-dose at Weeks 4, 8, and 12.

3.4.4. Serum unbound and total concentrations of GDF-15 on Day 1, Weeks 4, 5, 8, 10, 12, and 16 (follow-up), plus Week 9 and 11 in PK substudy only

Blood samples will be collected for measurement of serum concentrations of total and unbound GDF-15 at time points specified in the protocol. The GDF-15 sample collection at the Week 5 visit is considered an optional sample. It will not be considered a protocol deviation if the participant is unable to make this visit. In addition, if a participant has an unplanned site visit for any reason, (chemotherapy, radiology, other doctor appointments, etc.), a GDF-15 sample may be collected, if feasible.

Change from baseline and fold change from baseline (i.e. post-dose / baseline), for total and unbound GDF-15, will be calculated for all post-baseline timepoints.

Additionally, the unbound GDF-15 will be compared to the median healthy volunteer level, at all timepoints, to create an endpoint with two levels ('Yes' and 'No') indicating whether the concentration is below the estimated healthy volunteer median level (< 0.3ng/mL) or not (≥ 0.3ng/mL).

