## 2.2.1.4. Summary of GDF-15 Response

In study C3651001, following single SC administration of 1 to 300 mg doses of ponsegromab to healthy non-Japanese adults, the median duration of serum unbound GDF-15 suppression (defined as last time post-dose with unbound GDF-15 concentration reported as below LLOQ which was 42.4 pg/mL) increased with increasing dose of ponsegromab, ranging from 0.17 day for the 1 mg dose group to 75.61 days for the 300 mg dose group. There was generally no change from baseline in measures of unbound GDF-15 in participants treated with placebo, ponsegromab 0.1 and 0.3 mg groups. Following a single SC administration of ponsegromab 100 mg in healthy Japanese adult participants in study C3651002, serum unbound GDF-15 concentrations were suppressed to below the LLOQ starting on Day 1, with the median duration of suppression of 40.49 days, ranging from 9.00-88.07 days in individual participants.

In study C3651009, following SC administration of ponsegromab at 200 mg Q3W through Week 12 (Day 85) in participants with cancer, cachexia and elevated serum GDF-15 concentrations, median unbound GDF-15 concentrations were suppressed from the baseline concentration of 2269 pg/mL to below the LLOQ at all visits between Day 1 and Week 15 (Day 106).

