#### 4.2. Scientific Rationale for Study Design

The purpose of this study is to evaluate the efficacy, safety, and tolerability of ponsegromab, an inhibitor of GDF-15, compared to placebo, in patients with cancer, cachexia, and elevated concentrations of GDF-15.

Elevated concentrations of circulating GDF-15 have been reported in literature in patients experiencing weight loss with a variety of tumor types and a greater magnitude of elevation was associated with worse survival. Biospecimens from healthy adults (n=739) and patients with cancer (from both external commercial biorepositories and an internal study) were analyzed for GDF-15 concentrations. The cancer sample set contained 399 NSCLC, 116 pancreatic cancer, and 157 colorectal cancer patients. Analysis of both the cancer and healthy sample sets using the Roche Elecsys assay, confirmed literature reported elevations in GDF-15 concentrations in NSCLC, PANC, and CRC patients in comparison to healthy subjects (approximately 4-fold, 5-fold, and 4-fold, respectively). An ad-hoc analysis of samples from NSCLC patients from an internal Pfizer study demonstrated that higher GDF-15 concentrations were associated with a reduction in body weight. These data were also used to determine the GDF-15 inclusion criteria for this study to be the 95th percentile of GDF-15 concentrations reported in these healthy subjects (≥1.5 ng/mL).

In addition, published clinical data and internal animal model data suggest that administration of platinum therapy can induce increases in serum GDF-15 concentrations. Clinical literature and internal animal model data also suggest that the nausea, emesis and anorexia observed with platinum therapy may be mediated, at least in part, by platinum induced- elevations in GDF-15.

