Sparse unbound and total ponsegromab and GDF-15 concentrations will be measured in this study to (1) characterize ponsegromab PK in this population; (2) assess the range of baseline GDF-15 values and variability in this population; (3) characterize the dose/exposure-GDF-15 response after ponsegromab treatment in this population, and (4) evaluate GDF-15 suppression effect on body weight response. Participants enrolled in the PK substudy will have additional PK and PD assessments to enhance PK/PD characterization. As ponsegromab is a monoclonal antibody, immunogenicity samples will be collected for the determination of ADA and NAb.

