#### 4.3. Justification for Dose

In the part A of this study, ponsegromab will be administered with 100, 200, or 400 mg Q4W SC for a total of 3 doses. The proposed doses were determined based on all relevant information obtained from nonclinical safety studies and clinical data (including safety, tolerability, PK and PD) available. These clinical data included data from 2 completed studies in healthy participants (C3651001 and C3651002, see IB), clinical data (including safety, tolerability, PK, and PD) from the phase 1b study in cancer cachexia patients (C3651009), and the expected duration of GDF-15 suppression, defined as the time it suppress GDF-15 to below the median observed in healthy subjects (0.71 ng/mL).

The median baseline GDF-15 in NSCLC, PANC, and CRC patients are expected to be approximately 3.02, 3.32, and 3.50 ng/mL, respectively, and the 95th percentile are expected to be 8.69, 9.35, and 13.4 ng/mL, respectively. It is assumed that the composition of the cancer types will be similar to that observed in study C3651009, which is 4:4:3 for NSCLC, CRC, and PANC, respectively. Based on preliminary population PK/PD simulations, the proposed 100 mg Q4W SC dose is expected to suppress the unbound GDF-15 concentration in ~64%, and ~28% of the assumed cancer cachexia patients for 2, and 4 weeks, respectively. The proposed 200 mg Q4W SC dose is expected to suppress the unbound GDF-15 concentration in ~92%, and ~72% of the cancer cachexia patients for 2, and 4 weeks, respectively. The proposed high dose of 400 mg Q4W SC dose is expected to suppress the unbound GDF-15 concentration in >90% of the cancer cachexia patients for 4 weeks.

Based on these preliminary PK/PD simulations, the predicted steady state total ponsegromab Cmax, AUCtau, and Cavg, following 100, 200, and 400 mg Q4W SC doses, along with the corresponding safety margins calculated using exposure data from the 6-month toxicology study in monkeys (See IB), and exposure multiples calculated using total exposure data following a single 300 mg SC dose to healthy participants in study C3651001 are summarized in Table 3. The corresponding steady state unbound ponsegromab exposures and exposure multiples calculated using unbound exposure data from study C3651001, are summarized in Table 4.

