## 8.7.1. GDF-15

Blood samples of approximately 6 mL, to provide a minimum of 2 mL serum, will be collected for measurement of serum concentrations of total and unbound GDF-15 at time points specified in the SoA. The GDF-15 sample collection at the Week 5 visit is considered an optional sample. It will not be considered a protocol deviation if the participant is unable to make this visit. In addition, if a participant has an unplanned site visit for any reason, (chemotherapy, radiology, other doctor appointments, etc.), a GDF-15 sample may be collected, if feasible, provided the total volume taken during the study does not exceed 550 mL during any period of 56 consecutive days.

At the Screening visit, two GDF-15 samples will be collected (6-mL for each). One GDF-15 (Roche) sample will be analyzed using the IUO Roche Elecsys GDF-15 assay, for determination of enrollment eligibility. In addition, this sample may be used to help support development of a potential companion diagnostic test for ponsegromab. This screening assay will be validated in a CLIA accredited central laboratory. The second Screening GDF-15 (Pfizer) sample, as well as the GDF-15 samples collected at the other time points specified in the SoA, will be analyzed for unbound and total GDF-15 using validated Pfizer assays in compliance with applicable SOPs.

Instructions for the collection and handling of biological samples will be provided in the laboratory manual or by the sponsor. The actual date and time (24-hour clock time) of each sample will be recorded.

The actual times may change, but the number of samples will remain the same. Collection of samples within the protocol-allowed visit window, as defined in the SoA or above will not be captured as a protocol deviation, as long as the exact time of the collection is noted on the source document and the CRF.

Sample will be used to evaluate the PD of ponsegromab. Samples collected for PD analyses may also be used to evaluate safety or efficacy aspects related to concerns arising during or after the study, and/or evaluation of bioanalytical methods, or for other internal exploratory purposes.

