
A listing of unbound and total GDF-15 serum concentration levels, sorted by treatment group, participant and timepoint, will be produced. The listing will also include the fold change from baseline and will include all participants and all timepoints. For unbound GDF-15, the listing will also include a column to indicate whether the absolute GDF-15 concentration is below the healthy volunteer median level or not.

Additionally, the following presentations for unbound and total GDF-15 serum concentration levels will be produced, separately for 1) all participants (excluding Week 9 and 11 timepoints) and 2) for only participants in the PK substudy (including all timepoints):

- A summary of concentrations (absolute values and fold changes from baseline) by treatment group and timepoint, where the set of statistics will include (as data permit) n, arithmetic mean, SD, CV%, minimum, Q1, median, Q3, maximum, geometric mean, geometric CV% and the number of concentrations above the LLQ
- A summary of whether the absolute unbound GDF-15 concentrations are below the healthy volunteer median level or not, by treatment group and timepoint, as described in Section 5.2.2
- Median concentration-time plots (for absolute values only) (on a linear scale, all treatments on the same plot), Q1 and Q3 may be included
- Mean (±SD, if appropriate) concentration-time plots (for absolute values only) (on a linear scale, all treatments on the same plot).

In all presentations, the fold changes will be presented as percent change from baseline ([fold change from baseline -1]*100).

Note that the separate presentations for the participants in the PK substudy may be reported in a supplemental CSR rather than the main CSR.

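### Does the SAP's 0.3 ng/mL healthy-volunteer GDF-15 cut-off conflict with the 0.71 ng/mL healthy median in the protocol's dose justification?

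*SAP*

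**What the plan says.** Protocol 4.3 (Justification for Dose) takes account of how long suppression should last, which it says is "defined as the time it suppress GDF-15 to below the median observed in healthy subjects (0.71 ng/mL". It then gives simulated results that it calls preliminary. For the lowest dose the text reads "the proposed 100 mg Q4W SC dose is expected to suppress the unbound GDF-15 concentration in ~64%, and ~28% of the assumed cancer cachexia patients"; the two percentages refer to durations of 2 and 4 weeks. The matching figures are about 92% and 72% at 200 mg and, at 4 weeks only, more than 90% at 400 mg.

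SAP 3.4.4 creates a two-level variable for unbound GDF-15, according to whether the value is "below the estimated healthy volunteer median level (< 0.3ng/mL) or not (≥ 0.3ng/mL". SAP 6.4.4 plans "A summary of whether the absolute unbound GDF-15 concentrations are below the healthy volunteer median level or not, by treatment group and timepoint", without repeating the number.

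Two assay families appear in the protocol. Section 4.2 describes "Analysis of both the cancer and healthy sample sets using the Roche Elecsys assay". Section 8.7.1 says that the second screening sample and all later samples "will be analyzed for unbound and total GDF-15 using validated Pfizer assays in compliance with applicable SOPs". Neither 4.3 nor SAP 3.4.4 says which assay its healthy median came from.

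**The concern.** Both documents call their figure a healthy median, yet the figures differ more than twofold and nothing connects them. One stated purpose of the sampling in Protocol 4.2 is to "characterize the dose/exposure-GDF-15 response after ponsegromab treatment in this population". A reader could therefore set the SAP table beside the 4.3 predictions. If 50% of the 200 mg arm fell below the SAP cut-off, against a predicted 72%, the table alone would not show whether suppression was weaker than expected or the cut-off was simply stricter. At stake is the reading of one exploratory pharmacodynamic table. Comparisons between doses within that table use a single cut-off and hold either way.

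**Working it through.** **1. The gap.** 0.71 / 0.3 = 2.37.

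**2. Which scale does 0.71 sit on?** Protocol 4.3 expects baseline medians of 3.02 (NSCLC), 3.32 (PANC) and 3.50 ng/mL (CRC). Protocol 4.2 reports Roche elevations over healthy subjects of about 4-, 5- and 4-fold.

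| Tumour | Median / 0.71 | Median / 0.3 | Fold in 4.2 |
|---|---|---|---|
| NSCLC | 4.3 | 10.1 | ~4 |
| PANC | 4.7 | 11.1 | ~5 |
| CRC | 4.9 | 11.7 | ~4 |

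So 0.71 is broadly consistent with the Roche data (CRC fits less well) and 0.3 is not. This is inference; the documents do not say so.

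**3. Does unbound GDF-15 run lower?** Protocol 2.2.1.4 gives a median baseline unbound value of 2,269 pg/mL (2.269 ng/mL) in the Phase 1b cachexia study. Against the 4.3 medians, 2.269/3.50 = 0.65 and 2.269/3.02 = 0.75. Applied to 0.71, these ratios give 0.46 to 0.53 ng/mL. The direction matches a lower healthy median on the unbound scale, but this accounts for only part of the gap. Ten participants were dosed in that study, so the ratio is rough.

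**4. The worst case: both values on one scale.** The simulations behind 4.3 cannot be reproduced, because their parameters are not given. As an illustration, assume lognormal troughs with log-SD s. Then P(<0.3) = Φ(Φ⁻¹(P(<0.71)) − ln(2.37)/s), with ln(2.37) = 0.861. Take s = 0.63, the smallest baseline spread implied by 4.3 (PANC: ln(9.35/3.32)/1.645), and s = 2.0, an assumed upper bound.

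| Dose, share below 0.71 at 4 weeks | Below 0.3, s = 0.63 | Below 0.3, s = 2.0 |
|---|---|---|
| 100 mg, 28% | 3% | 16% |
| 200 mg, 72% | 22% | 56% |
| 400 mg, 90% (floor of >90%) | 47% | 80% |

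**5. Is that illustration credible?** The same model fixes the median trough at 0.71 × exp(−s × Φ⁻¹(p)). At 200 mg, Φ⁻¹(0.72) = 0.583, which gives 0.49 ng/mL (s = 0.63) or 0.22 ng/mL (s = 2.0). These are about 12 and 5 times the Phase 1 quantification limit ("unbound GDF-15 concentration reported as below LLOQ which was 42.4 pg/mL", or 0.0424 ng/mL). Yet Protocol 2.2.1.4 reports that, in patients with cancer cachexia on 200 mg every 3 weeks, the median unbound value was below the quantification limit at all visits from Day 1 to Week 15. A 200 mg median of 0.0424 or lower with 72% below 0.71 needs s of at least ln(0.71/0.0424)/0.583 = 2.818/0.583 = 4.8. The share below 0.3 is then at least Φ(0.583 − 0.861/4.8) = 66%, against 72%. The Phase 1b interval was 3 weeks rather than 4, so this does not settle the matter. It does suggest that the table in step 4 exaggerates the reclassification.

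**6. Would one common cut-off make the comparison valid?** No. The 4.3 figures describe suppression lasting 2 or 4 weeks, in an assumed 4:4:3 mix of NSCLC, CRC and PANC. The SAP table shows status at a visit, in whatever mix enrols. Outside the PK substudy the Week 10 visit has a ±7-day window, so that sample falls roughly 1 to 3 weeks after the Week 8 dose.

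**7. What else is reported?** SAP 6.4.4 gives minimum, Q1, median, Q3 and maximum of the absolute unbound concentrations by arm and timepoint, together with a listing of all values. If the scales are common and Q3 is below 0.71, at least about 75% of that arm is below the 4.3 threshold.

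**The case for a change.** The best case for a change is that the innocent explanation is not written down. No passage bridges the two assays or says which scale the 4.3 predictions use, SAP 2.1 lists no modifications to the protocol plan, and the SAP version history does not explain 0.3. Step 3 recovers only 0.46 to 0.53, so equivalence cannot be assumed. Both cut-offs lie well above the Phase 1 quantification limit (0.3/0.0424 = 7 times and 0.71/0.0424 = 17 times), so any samples between them would be measured and would change class.

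All of that stands as a remark on documentation. It does not show that either number is wrong or that an analysis run as written would mislead. The 0.71 figure belongs to a dose rationale. The protocol's endpoint is the concentrations themselves, and Protocol 9.3.4 leaves exploratory analyses to the SAP. The dose/exposure-response purpose is served by the concentration and fold-change summaries and by the optional population PK/PD analysis, none of which needs a cut-off.

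**Conclusion.** No change is called for. The two healthy medians do differ by a factor of 2.4 without explanation, but this is missing provenance for a descriptive flag. If 0.3 is the unbound-assay counterpart of 0.71, the effect is nil. If both are on one scale, the flag is stricter than the 4.3 definition by an amount that the documents cannot pin down, and the lognormal figures in step 4 should not be relied on. In either case the quartiles and listings in SAP 6.4.4 let a reader apply the other threshold, within-table dose comparisons hold, and the primary analysis, power and type I error are untouched. A statistician producing the table would print the number and note its assay as routine labelling. This rests on the concentration summaries being produced as planned, and on nobody treating the flag as a formal test of the 4.3 simulations, which no document proposes.

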3.4.5. Incidence of ADA and NAb

Blood samples will be collected for determination of ADA and NAb as specified in the protocol. See Appendix 7 for immunogenicity terms and definitions.

3.4.6. Change from baseline score for PROMIS-Fatigue at Week 12

The PROMIS Fatigue 7a is a self-reported measure that assesses a range of symptoms in the past 7 days from mild subjective feelings of tiredness to an overwhelming, debilitating, and sustained sense of exhaustion that likely decreases one's ability to execute daily activities and function normally in family or social roles.

The short form 7A consists of 7 items that study participants will rate from 1 to 5. A global raw score ranging from 7 to 35 is calculated and can be translated into a T score (Mean = 50, standard deviation (SD) = 10) using the Fatigue 7a Short Form score conversion table, provided in Appendix 3.

Change from baseline for PROMIS-Fatigue T-score will be calculated for all post baseline timepoints.

3.4.7. Change from baseline score for PROMIS-Physical Function at Week 12

The PROMIS Physical Function short form 8C is a self-reported 8 item measure that assesses capability rather than actual performance of physical activities. It includes the functioning of one's upper extremities (dexterity) and lower extremities (walking and mobility), as well as instrumental activities of daily living.

A single Physical Function capability score is obtained from a short form. A global raw score ranging from 8 to 40 is calculated and can be translated into a T score (Mean = 50, SD = 10) using the Physical Function Short Form 8c score conversion table, provided in Appendix 3.

Change from baseline for PROMIS-Physical Function T-score will be calculated for all post baseline timepoints.

3.4.8. Patient's Global Impression of Change (PGI-C) at Week 12; Change from baseline in Patient's Global Impression of Severity (PGI-S) at Week 12

3.4.8.1. PGI-C

The PGI-C consists of 5 questions that ask the study participants to rate the overall change in their level of appetite, fatigue, physical function, physical activity and walking since they started taking the study intervention on a 5-point verbal rating scale that ranges from "Much better" to "Much worse".

The PGI-C is recommended by FDA for use as an anchor measure to generate an appropriate threshold that represents meaningful within-individual change in the target patient population.

